7.7 Concomitant Therapy

Medications or vaccinations specifically prohibited in the exclusion criteria are not allowed during the ongoing trial. If there is a clinical indication for any medication or vaccination specifically prohibited during the trial, discontinuation from trial therapy or vaccination may be required. The investigator should discuss any questions regarding this with the Sponsor Clinical Director. The final decision on any supportive therapy or vaccination rests with the investigator and/or the participant's primary physician. However, the decision to continue the participant on study treatment requires the mutual agreement of the investigator, the Sponsor and the participant.

Listed below are specific restrictions for concomitant therapy during the course of the trial:

- Antineoplastic systemic chemotherapy or biological therapy
- Immunotherapy not specified in this protocol
- Chemotherapy not specified in this protocol
- Investigational agents other than pembrolizumab

- Radiation therapy
- Live vaccines within 30 days prior to the first dose of study treatment and while participating in the trial. Examples of live vaccines include, but are not limited to, the following: measles, mumps, rubella, varicella/zoster (chicken pox), yellow fever, rabies, Bacillus Calmette-Guérin, and typhoid vaccine. Seasonal influenza vaccines for injection are generally killed virus vaccines and are allowed; however, intranasal influenza vaccines (eg, FluMist[®]) are live attenuated vaccines and are not allowed.
- Systemic glucocorticoids for any purpose other than to modulate symptoms from an AE that is suspected to have an immunologic etiology. The use of physiologic doses of corticosteroids may be approved after consultation with the Sponsor.

Note: Use of prophylactic corticosteroids to avoid allergic reactions (eg, IV contrast dye or transfusions) is permitted.

Note: The use of intermittent inhaled steroids or intranasal or local injection of corticosteroids is permitted.

Participants who, in the assessment by the investigator, require the use of any of the aforementioned treatments (excluding the exceptions noted above) for clinical management should be removed from the trial. Participants may receive other medications that the investigator deems to be medically necessary.

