8.1 Discontinuation of Study Treatment

Discontinuation of study treatment does not represent withdrawal from the study.

As certain data on clinical events beyond study treatment discontinuation may be important to the study, they must be collected through the participant's last scheduled follow-up, even if the participant has discontinued study treatment. Therefore, all participants who discontinue study treatment prior to completion of the protocol-specified treatment period will still continue to participate in the study as specified in Section 2 - SoA and Section 9.10.4 – Discontinued Participants Continuing to be Monitored in the Study, unless the participant withdraws from the study.

Participants may discontinue study treatment at any time for any reason or be dropped from the study treatment at the discretion of the investigator should any untoward effect occur. In addition, a participant may be discontinued from study treatment by the investigator or the Sponsor if study treatment is inappropriate, the trial plan is violated, or for administrative and/or other safety reasons. Specific details regarding procedures to be performed at study treatment discontinuation are provided in Section 9.1.9 – Withdrawal/Discontinuation.

A participant must be discontinued from study treatment but continue to be monitored in the study for any of the following reasons:

- The participant or participant’s legally acceptable representative requests to discontinue study treatment.
- Participants with AEs meeting discontinuation criteria as described in Section 9.
- The participant has a medical condition or personal circumstance or is noncompliant to study treatments or procedures, which, in the opinion of the investigator and/or Sponsor, place the participant at unnecessary risk from continued administration of study treatment.
- The participant has a confirmed positive serum pregnancy test.
- The participant has received 17 cycles of study treatment.
- Any progression or recurrence of the malignancy under study.

NOTE: All scans for the participant must be submitted to the central imaging vendor according to the Procedures Manual. Clinically stable participants that are first identified with disease recurrence may remain on study treatment while waiting for confirmation of recurrence by the investigator (Section 9.2.1).

- A new malignancy requiring active treatment.

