8.2 Withdrawal from the Study

A participant must be withdrawn from the study if the participant or participant's legally acceptable representative withdraws consent from the study.

If a participant withdraws from the study, they will no longer receive study treatment or be followed at scheduled protocol visits.

Specific details regarding procedures to be performed at the time of withdrawal from the study including the procedures to be performed should a participant repeatedly fail to return for scheduled visits and/or if the study site is unable to contact the participant, as well as specific details regarding withdrawal from Future Biomedical Research are outlined in Section 9.1.9 – Withdrawal/Discontinuation.

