9.1.5.2.1 Poststudy Anticancer Therapy

If a participant initiates a new anticancer therapy while receiving study treatment, study treatment must be discontinued and the participant will move into the Survival Follow-up phase. If a participant initiates a new anticancer therapy within 30 days after the last dose of study treatment, the End of Treatment Visit and the 30-day Safety Follow-up Visit must occur before the first dose of the new therapy. All new anticancer therapy initiated after the study start must be recorded in the poststudy anticancer therapy eCRF.

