9.1.9 Withdrawal/Discontinuation

Participants who discontinue study treatment prior to completion of the treatment period should be encouraged to continue to be followed for all remaining study visits.

When a participant discontinues/withdraws from participation in the trial, all applicable activities scheduled for the End of Treatment Visit should be performed at the time of discontinuation. Any adverse events which are present at the time of discontinuation/withdrawal should be followed in accordance with the safety requirements outlined in Section 9.3 - Adverse Events, Serious Adverse Events, and Other Reportable Safety Events. Participants who complete 17 cycles of study treatment (approximately 1 year) must discontinue treatment. After discontinuing treatment period, all participants should return to the site for the End of Treatment Visit and Safety Follow-up visit and then proceed to Efficacy Follow-up (described in Section 9.10.3).

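### Section 7.7 tells sites to remove from the trial participants who need a restricted treatment, whereas the rest of the protocol stops study treatment and keeps them in follow-up

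*Combined protocol and SAP*

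**What the plan says.** Section 7.7 (Concomitant Therapy) lists what is restricted: antineoplastic systemic therapy, immunotherapy and chemotherapy outside the protocol, other investigational agents, radiation, live vaccines, and systemic glucocorticoids with some exceptions. The paragraph after the list says that participants who in the investigator's assessment need "any of the aforementioned treatments (excluding the exceptions noted above) for clinical management should be removed from the trial". The opening of the section is milder. If a prohibited medication or vaccine is indicated, "discontinuation from trial therapy or vaccination may be required", and study treatment may continue if investigator, Sponsor and participant all agree.

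The sections that govern discontinuation and follow-up say:

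- **8.1:** "Discontinuation of study treatment does not represent withdrawal from the study". It adds that "all participants who discontinue study treatment prior to completion of the protocol-specified treatment period will still continue to participate in the study", unless they withdraw.
- **8.2:** withdrawal is compulsory when the participant or the participant's "legally acceptable representative withdraws consent from the study". The consequence is spelled out: "If a participant withdraws from the study, they will no longer receive study treatment or be followed at scheduled protocol visits".
- **9.1.9:** those who stop treatment early "should be encouraged to continue to be followed for all remaining study visits".
- **9.1.5.2.1:** if new anticancer therapy starts during study treatment, "study treatment must be discontinued and the participant will move into the Survival Follow-up phase".
- **9.10.5:** people who stop for any reason other than recurrence stay on study with their regular assessments.
- **Synopsis:** everyone is followed for OS until death, withdrawn consent or study end.

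**The concern.** One event, the need for a restricted treatment, has two different consequences. Under Section 8.1 the participant stops treatment at most and stays in follow-up. Under the later sentence of Section 7.7 the participant leaves the trial.

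The difference matters because DFS and OS are analysed in all randomized participants (Section 10.5.1). Someone removed without an event is censored at the last disease assessment for DFS (Table 10) and at the last date known alive for OS (Table 11). The current primary DFS rule counts events even after missed assessments or new anticancer treatment, so the analysis relies on follow-up continuing after treatment stops. Literal removal works against that. If the need for a restricted treatment were related to prognosis, the censoring could be informative. Nothing in the documents shows that it is.

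**Working it through.** **Does the wording conflict?** The protocol generally uses study treatment and trial as different things. Section 6.5 names stopping study treatment and withdrawing from the trial as alternatives. Section 8.1 speaks of people taken off treatment who are still monitored in the trial. On that usage, removal from the trial means the end of monitoring. The only exit for which the protocol describes a loss of scheduled visits is withdrawal under Section 8.2, and the ground given there is withdrawn consent, not a concomitant treatment.

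**Who is exposed?**

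- Section 7.7 states that nothing is prohibited in post-treatment follow-up, so only the treatment period (17 cycles, about one year) counts.
- New anticancer therapy is covered by Section 9.1.5.2.1, and imaging stops then anyway under Section 9.2.1.3.
- Steroids for suspected immune-related adverse events are exempt, as are prophylactic, inhaled, intranasal and locally injected steroids.
- What remains is mainly non-exempt systemic steroids, live vaccines, and radiation or other agents not given as anticancer therapy.

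**Reproducing the plan's power.** Inputs from Section 10.9 and Tables 14 and 15: HR 0.67, one-sided alpha 2.5%, 1:1 allocation, DFS looks at 265 and 332 events, OS looks at 94, 132, 172 and 200 deaths. The mean of the test statistic at *d* events is √(*d*/4) × |ln HR|.

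- DFS, single look: √(332/4) × 0.4005 = 3.65; power = Φ(3.65 − 1.96) = 95.4%.
- DFS, two looks with the Table 14 bounds: 95.1% (the plan says about 95%; Table 14 gives 0.9490).
- OS, four looks with the Table 15 bounds: 79.7% (the plan says about 79%; Table 15 gives 0.7930).

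**Scale per 1% removed.** The documents give no rate of use, so 1% is an arbitrary unit. The lost events are taken at the trial-average proportion, with nothing recovered.

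- Participants: 1% × 990 = 9.9.
- Deaths: 9.9 × 200/990 = 2.0.
- DFS events: 9.9 × 332/990 = 3.3.

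The final looks are event-driven, so the main consequence is delay:

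- OS pace between the last two looks: (200 − 172)/(72 − 63) = 3.11 deaths per month; 2.0/3.11 = 0.6 months.
- DFS pace: (332 − 265)/(50 − 39) = 6.09 events per month; 3.32/6.09 = 0.5 months.
- At 5% removed (49.5 people): 10 deaths, and 10/3.11 = 3.2 months for the final OS look.

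If the looks were instead held at their planned calendar times:

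| Events lost | DFS power | OS power |
|---|---|---|
| none | 95.1% | 79.7% |
| 1% | 94.9% | 79.3% (79.4% if bounds are recomputed by the spending function) |
| 5% | 94.1% | 77.6% |

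The 5% row keeps the published bounds. All these losses are upper limits for the stated percentage, because events before removal would still count and some deaths would be found by other means.

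**The case against.** The best reply is that the protocol already settles the outcome. Section 8.1 is the governing section. Its list of reasons for stopping treatment while monitoring continues includes medical conditions and the investigator's decision, and Sections 9.1.9, 9.10.2 and 9.10.5 repeat the principle. The phrase from the trial is also used loosely elsewhere: Section 9.5.4.2 discontinues pregnant participants from the trial, although Section 8.1 keeps them monitored. Section 7.7 sends questions to the Sponsor Clinical Director. For OS, Section 9.10.6 lets the Sponsor request survival status for every participant without a scheduled contact, so zero recovery of deaths is pessimistic. The removal rates are hypothetical, and the 1% power changes are no larger than the gaps between the recalculated and tabulated power.

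Most of this stands, and it is why the point is minor. Two qualifications about the other sections are also fair. Section 9.1.5.2.1 makes stopping study treatment mandatory and leads to survival follow-up only. Section 8.2 supports continued follow-up by implication rather than by stating it.

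None of this removes the conflict. The parallel pregnancy wording shows that the protocol is ambiguous on this term; it does not tell a site which reading to use. A site reading Section 7.7 alone finds an instruction to remove the participant, and survival checks cannot restore missed scans.

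**Conclusion.** The concern holds. The sentence in Section 7.7 contradicts that section's own opening, Sections 8.1, 9.1.9 and 9.10.5, and the synopsis. It is a minor wording conflict that affects a limited group during the treatment year. Harm is conditional on a site following this sentence over Section 8.1, and the documents do not show that any site did. The number affected and any bias from informative censoring cannot be derived. The event and delay figures rest on assumed removal rates, trial-average event proportions and no recovery of lost events. On those terms the effect on power is negligible. The reason to act is consistent retention of randomized participants.

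**What to change.** In Section 7.7, replace the instruction to remove with wording such as: *should be discontinued from study treatment, unless its continuation is agreed as described above, and should continue to be followed in the study per Sections 8.1, 9.1.5.2.1, 9.2.1.3 and 9.10.* This keeps the mutual-agreement route and sends new anticancer therapy to its existing rule. The similar phrase in Section 9.5.4.2 could be aligned in the same edit.

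Also ask sites once whether anyone was removed under Section 7.7, and resume follow-up where consent stands. Section 10.9 refers to the actual final number randomized, which suggests that enrolment is complete or nearly so. That is an inference, but if it is right, the query is probably worth more than the edit.

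The cost is one sentence, which can go into the next amendment, and one site query. The follow-up schedule already exists. No sample size, event target, boundary or power figure changes.

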7.7.1 Rescue Medications & Supportive Care

Participants should receive appropriate supportive care measures as deemed necessary by the treating investigator. Suggested supportive care measures for the management of AEs with potential immunologic etiology are outlined along with the dose modification guidelines in Section 7.2, [Table 5](#) and [Table 6](#). Where appropriate, these guidelines include the use of oral or IV treatment with corticosteroids, as well as additional anti-inflammatory agents if symptoms do not improve with administration of corticosteroids. Note that several courses of steroid tapering may be necessary as symptoms may worsen when the steroid dose is

decreased. For each disorder, attempts should be made to rule out other causes such as metastatic disease or bacterial or viral infection, which might require additional supportive care. The treatment guidelines are intended to be applied when the investigator determines the events to be related to pembrolizumab.

Note: If after the evaluation of the event, it is determined not to be related to pembrolizumab, the investigator does not need to follow the treatment guidance. Refer to [Table 5](#) and [Table 6](#) in Section 7.2 for guidelines regarding dose modification and supportive care.

It may be necessary to perform conditional procedures such as bronchoscopy, endoscopy, or skin photography as part of evaluation of the event.

7.8 Treatment After the End of the Study

There is no study-specified treatment following the end of the study.

7.9 Clinical Supplies Disclosure

This trial is blinded but supplies are provided open label; therefore, an unblinded pharmacist or qualified trial site personnel will be used to blind supplies. Study treatment identity (name, strength or potency) is included in the label text; random code/disclosure envelopes or lists are not provided.

The emergency unblinding call center will use the treatment/randomization schedule for the trial to unblind participants and to unmask study treatment identity. In the event that the emergency unblinding call center is not available for a given site in this trial, the central electronic treatment allocation/randomization system (IVRS/IWRS) should be used in order to unblind participants and to unmask study treatment identity. The Sponsor will not provide random code/disclosure envelopes or lists with the clinical supplies.

See Section 9.1.10, Participant Blinding/Unblinding, for a description of the method of unblinding a participant during the trial, should such action be warranted.

8. Discontinuation/Withdrawal Criteria

8.1 Discontinuation of Study Treatment

Discontinuation of study treatment does not represent withdrawal from the study.

As certain data on clinical events beyond study treatment discontinuation may be important to the study, they must be collected through the participant's last scheduled follow-up, even if the participant has discontinued study treatment. Therefore, all participants who discontinue study treatment prior to completion of the protocol-specified treatment period will still continue to participate in the study as specified in Section 2 - SoA and Section 9.10.4 – Discontinued Participants Continuing to be Monitored in the Study, unless the participant withdraws from the study.

Participants may discontinue study treatment at any time for any reason or be dropped from the study treatment at the discretion of the investigator should any untoward effect occur. In addition, a participant may be discontinued from study treatment by the investigator or the Sponsor if study treatment is inappropriate, the trial plan is violated, or for administrative and/or other safety reasons. Specific details regarding procedures to be performed at study treatment discontinuation are provided in Section 9.1.9 – Withdrawal/Discontinuation.

A participant must be discontinued from study treatment but continue to be monitored in the study for any of the following reasons:

- The participant or participant’s legally acceptable representative requests to discontinue study treatment.
- Participants with AEs meeting discontinuation criteria as described in Section 9.
- The participant has a medical condition or personal circumstance or is noncompliant to study treatments or procedures, which, in the opinion of the investigator and/or Sponsor, place the participant at unnecessary risk from continued administration of study treatment.
- The participant has a confirmed positive serum pregnancy test.
- The participant has received 17 cycles of study treatment.
- Any progression or recurrence of the malignancy under study.

NOTE: All scans for the participant must be submitted to the central imaging vendor according to the Procedures Manual. Clinically stable participants that are first identified with disease recurrence may remain on study treatment while waiting for confirmation of recurrence by the investigator (Section 9.2.1).

- A new malignancy requiring active treatment.
NOTE: In the event that a new malignancy is diagnosed and requires active treatment, the Sponsor should be consulted as to whether the participant should be discontinued from study treatment.
- Intercurrent illness other than another malignancy as noted above that prevents further administration of treatment.
- Recurrent Grade 2 pneumonitis.
- Investigator’s decision to discontinue participant.

For information about the End of Treatment Visit and Safety Follow-up Visit, please refer to Section 9.10.3.

For participants who are discontinued from study treatment but continue to be monitored in the trial, all visits and procedures, as outlined in the SoA, should be completed.

Discontinuation from study treatment is “permanent.” Once a participant is discontinued, he/she shall not be allowed to restart study treatment.

8.2 Withdrawal from the Study

A participant must be withdrawn from the study if the participant or participant's legally acceptable representative withdraws consent from the study.

If a participant withdraws from the study, they will no longer receive study treatment or be followed at scheduled protocol visits.

Specific details regarding procedures to be performed at the time of withdrawal from the study including the procedures to be performed should a participant repeatedly fail to return for scheduled visits and/or if the study site is unable to contact the participant, as well as specific details regarding withdrawal from Future Biomedical Research are outlined in Section 9.1.9 – Withdrawal/Discontinuation.

8.3 Lost to Follow Up

If a participant fails to return to the clinic for a required study visit and/or if the site is unable to contact the participant, the following procedures are to be performed:

- o The site must attempt to contact the participant and reschedule the missed visit. If the participant is contacted, the participant should be counseled on the importance of maintaining the protocol-specified visit schedule.
- o The investigator or designee must make every effort to regain contact with the participant at each missed visit (e.g. phone calls and/or a certified letter to the participant's last known mailing address or locally equivalent methods). These contact attempts should be documented in the participant's medical record.
- o Note: A participant is not considered lost to follow up until the last scheduled visit for the individual participant. The amount of missing data for the participant will be managed via the pre-specified data handling and analysis guidelines.

9. Study Assessments and Procedures

- Study procedures and their timing are summarized in the SoA.
- Adherence to the study design requirements, including those specified in the SoA, is essential and required for study conduct.
- All screening evaluations must be completed and reviewed to confirm that potential participants meet all eligibility criteria. The investigator will maintain a screening log to record details of all participants screened and to confirm eligibility or record reasons for screening failure, as applicable.
- Procedures conducted as part of the participant's routine clinical management (eg, blood count) and obtained before signing of ICF may be utilized for screening or baseline purposes provided the procedure met the protocol-specified criteria and were performed within the time frame defined in the SoA.

Repeat or unscheduled samples and images may be taken for safety reasons or for technical issues with the samples.

